8.4. Derived and Computed Variables

The following derived and computed variables have been initially identified as important for the analysis of the primary and secondary target variables. It is expected that additional variables will be required. The SAP will not be amended for additional variables that are not related to the primary target or key secondary target variables. Any additional derived or computed variables will be identified and documented in the SAS programs that create the analysis files. If the SAP is not amended, further derivations related to primary and secondary target variables will be described in the CSR.

• Body Mass Index: BMI = (Body weight) / Height² [Unit: kg/m²]

• Response based on the adjusted INCAT disability score:

Yes, if [Score at week 24] ≤ [Score at Week 0] - 1 and patient did not receive rescue treatment; No otherwise (including patients discontinued before week 24 and patients receiving rescue treatment)

The same definition will be applied to other visits than week 24 to allow for an analysis of the time to first response. Time to first response will be censored at start date of rescue medication if a patient received rescue medication and did not show a response before. In case a patient did not show any response until termination visit and did not receive rescue medication, time to first response will be censored at termination visit.

Worsening with respect to INCAT disability score:

Worsening occurs if a patient score increases to at least 1 point above the Week 0 value.

• Response based on grip strength (Martin Vigorimeter):

Evaluate both hands. Yes, if [Strength at Week 24] \geq [Strength at Week 0] + 8kPa in the dominant or the non-dominant hand and patient did not receive rescue treatment; No otherwise (including patients discontinued before week 24 and patients receiving rescue treatment).

Response/Worsening based on the I-RODS score:

The individual Minimally Clinically Important Difference (MCID)-related SE (MCID-SE) score is derived for each visit and patient individually, and categorized as follows:

MCID-SE ≥ 1.96	clinically important improvement
0 < MCID-SE < 1.96	clinically unimportant improvement
MCID-SE = 0	no change
-1.96 < MCID-SE < 0	clinically unimportant deterioration
MCID-SE ≤ -1.96	clinically important deterioration

The individual MCID-SE values are computed through the Rasch person location values (logits) **R** associated with the I-RODS Summed Raw Scores as follows:

Overall patient response is defined as follows:

Yes, if clinically important improvement (i.e. MCID-SE ≥ 1.96) at week 24 and patient did not receive rescue treatment; No otherwise (including patients discontinued before week 24 and patients receiving rescue treatment).

Response based on the original MRC sum score [at Week 24]:

Yes, if increase from Week 0 by at least 4 points and patient did not receive rescue treatment; No otherwise (including patients discontinued before week 24 and patients receiving rescue treatment)

An analogue definition will be applied for response at Week 12.

Worsening based on the original MRC sum score:

Decrease to or below baseline value after temporary improvement by at least 4 points. Patients who did not temporarily improve by at least 4 points will be excluded from the analysis of time to first worsening.

Changes from baseline to termination visit in scales/scores:

When calculating those changes, values under rescue treatment will not be taken into account. Changes will be calculated to last value before start of rescue treatment.

• MRC sum score:

Though mentioned in the protocol, a modified version of the MRC sum score will not be calculated, as this modified version could not be established in other studies.

NCS measurements:

The following variables will be calculated from NCS measurements:

- Sum of all distal amplitudes: the sum will be calculated from 4 nerves, both right and left sides, for a total of 8 amplitudes. The distal sites are the ankle (lower limbs, peroneal and tibial nerves) and wrist (upper limbs, ulnar and median nerves).
- Sum of the proximal amplitudes: this will be a total sum of 6 parameters, as no proximal amplitude was measured for the tibial nerve. Proximal sites are at the fibular head (lower limb peroneal nerve) and elbow (upper limbs).
- Sum of conduction velocities (6 in total, as no conduction velocity was measured for tibial nerve)
- Sum of durations distal locations (8 in total)
- Sum of areas distal locations (8 in total)

For the last three variables, in case the result is NR (No response) in the data set, the worst value in the data set for the corresponding parameter and for the respective nerve will be used. Worst value is the highest value for durations, lowest value for area and lowest value for conduction velocity.

9. Study Subjects and Demographics

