4.2.3 Forbidden Concomitant Therapy

Corticosteroids may not be given as a pre-treatment to alleviate potential tolerability problems.

Administration of any other blood or plasma-derived product is forbidden and should only be given for emergency reasons. Patients will be withdrawn from the study if immunoglobulin preparations other than NewGam are administered.

- Corticosteroids (prednisolone or equivalent) > 20 mg/day or equivalent (i.e., > 40 mg every 2 days)
- PEX
- Cyclosporin, methotrexate, mitoxantrone, mycophenolate mofetil and interferon or other immunosuppressive or immunomodulatory drugs
- Rituximab, alemtuzumab, cyclophosphamide or other chemotherapeutic regimens
- Any experimental treatment
- Regulatory Authorities discourage the use of pre-medication in clinical trials designed to evaluate the safety of biologic products, except in cases where such pre-medication is important to the safety of the trial patients. Therefore any routine pre-medication to alleviate potential tolerability problems is disallowed. However, patients who experience 2 consecutive infusion-related AEs that are likely to be prevented by pre-medication are permitted to receive antipyretics, antihistamines, or antiemetic drugs. Non-steroidal anti-inflammatory drugs (NSAIDs) can affect renal function and should be avoided.

NewGam must not be mixed with other medicinal products; a separate intravenous line should be used in such cases.

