4.4 Withdrawal and Replacement of Patients

4.4.1 Premature Patient Withdrawal

For any discontinuation after study entry, the Investigator will obtain all the required details and document the reason(s) for discontinuation in the CRF. If the reason for withdrawal of a patient is an AE, the main specific event or laboratory test will be recorded in the CRF, and the Investigator will make thorough efforts to clearly document the outcome.

Patients have the right to withdraw from the study at any time for any reason, without the need to justify their decision. The Investigator also has the right to withdraw patients from the study in case of AEs, poor compliance, or other reasons. Since an excessive rate of withdrawal can render the study non-interpretable, the unnecessary withdrawal of patients must be avoided. Should a patient decide to withdraw, the Investigator will make the best efforts to complete and report the observations. The Investigator will document the reason(s) for withdrawal of each patient in the electronic Case Report Form (eCRF).

Patients who terminate the study prematurely are drop-outs. The Investigator has to organize the pre-termination visit.

Reasons for premature termination of patients may be:

- Withdrawal of patient’s consent (e.g. due to ineffective therapy in case of deterioration)
- Pregnant patients will be immediately excluded from the study

- Investigator's opinion that the patient may be severely harmed if he/she continues trial participation, namely by the treatment and procedures according to the study protocol
- Occurrence of a disease which interferes with the study treatment or represents an exclusion criterion
- Administration of IGIV other than NewGam.

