5.10 Relevant Protocol Deviations

Deviations from the protocol should not occur. If deviations occur, the Investigator should promptly inform the Monitor and the implication of the deviation must be reviewed and discussed. Any deviation must be documented, stating the reason and date, the action taken, and the impact for the patient and/or the trial. The documentation must be kept in the Investigator's Trial File and the Sponsor's file.

Examples of relevant protocol deviations that will be addressed are:

- Patients who entered the study even though they did not satisfy the entry criteria
- Patients who developed withdrawal criteria during the study
- Patients who received the wrong treatment or incorrect dose
- Patients who received an excluded concomitant treatment (e.g. IGIV other than NewGam).

In case of any major protocol deviations or violations the Investigator and Octapharma will decide on the further participation of the patient in this study, after having discussed all relevant aspects.

A list of all included patients with all deviations from the intended study procedures and other criteria that may affect the patient's validity for statistical analysis will be prepared upon clinical completion of the study. This will then be discussed by a panel consisting of the clinical project manager, a medical expert of the Sponsor, the data manager, the study biometrician and the Steering Committee. This panel will decide upon the membership of the patient in the ITT and PP efficacy and safety populations for statistical analysis.

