9.2.1 Population for Analysis

The following populations will be considered for the statistical analysis:

The safety set (SAF) will include all randomized patients who received at least part of one infusion of IMP.

The full analysis set (FAS) is defined according to the intention-to-treat principle, and will include all patients of the SAF who satisfy all major entry criteria – in particular the diagnosis of CIDP – and for whom any data was collected post infusion of IMP. Every treated subject will be considered in the analysis according to his randomized treatment/dose assignment.

The per-protocol set (PPS) – being a subset of the FAS — will exclude patients with significant protocol deviations, which may have an impact on the evaluation of the primary study outcome parameter(s). This is the set of patients who participated in the study as intended and for whom the primary efficacy endpoint can be evaluated as planned.

All protocol deviations documented during the conduct of the study or identified at the data review process prior to DB lock will be reviewed and classified with respect to its effect on the planned analysis. Only protocol violations with the potential to significantly affect the study results or to invalidate the interpretation of the data obtained will lead to exclusion of patients from the PPS. This classification of protocol violations is the joint responsibility of the clinical study manager, the study statistician, and Octapharma's responsible medical expert, and will be performed and documented before the database is locked, the data is unblinded, and the statistical analyses are performed.

Protocol deviations to be considered will include (but are not limited to):

- Deviations of the study entry criteria
- Administration of any other blood or plasma-derived product or of any other immunoglobulin preparations
- Any prohibited concomitant medication
- Failure to attend two scheduled consecutive visits OR three or more scheduled visits during the study for reasons other than clinical reasons

The analysis of safety will be based on the safety set.

The evaluation of primary objective(s) will be performed for the FAS (intention-to-treat analysis) and for the PPS (per-protocol analysis). The ITT analysis is considered to be the most relevant, and will be presented first in the statistical report.

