4.1. Overall Study Design and Plan

Study NGAM-08 is designed as a prospective, double-blind, randomized, multicenter phase III study. The rationale for conducting this study is to confirm the published clinical results obtained with the 1.0 g/kg dosing in order to apply for market authorization of NewGam, and to evaluate different dosing options on both sides of the standard dose with respect to efficacy and safety.

Patients will be screened for eligibility and, if eligible, thereafter have to decrease their current medication (Immunoglobulins by 25% from infusion to infusion or corticosteroids as per the discretion of the Investigator at a rate to expect study entry within 6-12 weeks) for a maximum of 12 weeks (Wash-out Phase). Only patients who deteriorate in this phase, i.e. active patients who need treatment, will be randomized 1:2:1 between three different dosages of NewGam (0.5 g/kg, 1.0 g/kg or 2.0 g/kg NewGam), and enter the Dose-Evaluation Phase.

[figure not shown]
The two allowed types of treatment prior to enrollment – Immunoglobulins or Corticosteroids – will be considered as strata in a stratified block design randomization with fixed block size. An electronic IWRS tool will be used to realize the randomization ratio of 1:2:1 with respect to the dosage groups, in each of the strata independently.

During the 24-week Dose-evaluation Phase all patients will first receive an initial loading dose of 2.0 g/kg NewGam, followed by 7 maintenance dosages of 0.5 g/kg, 1.0 g/kg or 2.0 g/kg NewGam every 3 weeks as they were randomized to.

Patients not deteriorating in the 12-week Wash-out Phase will not be enrolled into the ProCID study as they are not having active CIDP.

In addition the following rescue treatment option will be available: two consecutive infusions of 2.0 g/kg NewGam at 3-week intervals for all patients in the 0.5 and 1.0 g/kg NewGam arms who are either stable at Week 6 or deteriorate after Week 3 and before Week 18. Patients in the 2.0 g/kg NewGam arm will drop-out if they are stable at Week 6 or deteriorating after Week 3 and before Week 21.

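### The SAP scores NewGam rescue as non-response but has no such rule for other forbidden CIDP therapy, so an improved 1.0 g/kg patient who took it and stayed to Week 24 is a confirmatory responder

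*SAP*

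**What the plan says.** **Response rule.** SAP 8.4 requires a fall of at least 1 point on the adjusted INCAT score "and patient did not receive rescue treatment; No otherwise (including patients discontinued before week 24 and patients receiving rescue treatment". The grip strength, I-RODS and MRC response definitions carry the same condition. SAP 8.2 and 8.3 add that a missing Week 24 INCAT score is non-response in the FAS.

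**Meaning of rescue.** SAP 4.1: "In addition the following rescue treatment option will be available: two consecutive infusions of 2.0 g/kg NewGam at 3-week intervals". No other treatment is called rescue in either document.

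**Forbidden therapy.** Protocol 4.2.3 lists "Corticosteroids (prednisolone or equivalent) > 20 mg/day or equivalent (i.e., > 40 mg every 2 days", plasma exchange, "Cyclosporin, methotrexate, mitoxantrone, mycophenolate mofetil and interferon or other immunosuppressive or immunomodulatory drugs", and rituximab, alemtuzumab, cyclophosphamide or other chemotherapy.

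**Consequence of taking it.** Withdrawal is mandatory for one class only: "Patients will be withdrawn from the study if immunoglobulin preparations other than NewGam are administered". The list of termination reasons in protocol 4.4.1 likewise names just one treatment, "Administration of IGIV other than NewGam". For other major deviations, protocol 5.10 says that "the Investigator and Octapharma will decide on the further participation of the patient in this study".

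**Analysis sets.** The FAS in SAP 7 keeps every treated patient with any post-infusion data, and SAP 10 makes it the primary assessment. Protocol 9.2.1 lists "Any prohibited concomitant medication" among the deviations to be considered for exclusion from the per-protocol set (PPS).

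**The concern.** The SAP already treats added CIDP treatment as failure, but only when that treatment is more of the study drug. Protocol 1.1 and 3.3.2 describe corticosteroids and plasma exchange as beneficial in CIDP. Under the rule as written, extra NewGam fails a patient, while a different active treatment can leave that patient counted as a NewGam response.

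This matters more here than in a two-arm comparison. The confirmatory claim is one arm's rate against a fixed 42%, with no concurrent control in which the same contamination would appear. A corticosteroid-pretreated patient who may continue at a limited dose (protocol 4.2.2) and then exceeds the limit is a foreseeable case.

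**Working it through.** **1. Can such a patient reach the confirmatory numerator?** Take a 1.0 g/kg patient given plasma exchange or corticosteroids above the limit.
- Withdrawal is not mandatory (protocol 4.2.3, 4.4.1). Continuation is decided case by case (5.10).
- If the patient stays, the FAS includes them (SAP 7).
- If the Week 24 score is present and at least 1 point lower, and no NewGam rescue was given, SAP 8.4 returns Yes.
- If the patient leaves before Week 24, SAP 8.2 and 8.4 return No.

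The gap is therefore limited to patients who stay, are not rescued and are improved at Week 24.

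**2. Reproduce the plan's sample size.** Inputs from protocol 9.1 and SAP 6: threshold 0.42, assumed rate 0.60, 62 evaluable, 70 enrolled. The Wilson lower limit for x of n, with p = x/n and z = 1.96, is

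L = [p + z²/(2n) − z·√(p(1−p)/n + z²/(4n²))] / (1 + z²/n).

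Success needs L of at least 0.42; power is the exact binomial tail.
- n = 62: 34 responders needed, power 83.1%.
- n = 61: 34 needed, power 79.2%.
- Every n from 62 to 75 (the largest checked) gives at least 80%, so the plan's 62 is reproduced.
- n = 70: 38 needed, power 86.4%.

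**3. Boundary.** For 38/70, p = 0.5429 and L = (0.5429 + 0.0274 − 1.96 × 0.0612) / 1.0549 = 0.427, a success. For 37/70, L = 0.413, a failure. One reclassified patient reverses the result.

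**4. Effect on the false-success chance.** The documents give no frequency, so k, the average number of the 70 falsely counted as responders, is an assumption. With the true rate at 0.42, the counted rate is 0.42 + k/70, and the chance of success is P(X ≥ 38) for X binomial with n = 70.

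| k | counted rate | P(success) |
|---|---|---|
| 0 | 0.4200 | 2.6% |
| 1 | 0.4343 | 4.4% |
| 2 | 0.4486 | 7.2% |
| 3 | 0.4629 | 11.1% |
| 4 | 0.4771 | 16.3% |

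With n = 62 and 34 needed, the same k (as k/62) give 2.8%, 5.0%, 8.2%, 12.8% and 19.0%.

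**5. k is not the number of users.** If users were typical at the null, 58% would otherwise have failed. Even if all of them then improved, k = 1 to 4 would need 1/0.58 = 1.7 to 4/0.58 = 6.9 users, or 2.5% to 9.9% of 70.

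**6. Does the PPS catch it?** If one such patient were excluded and nobody else, 38/70 would become 37/69, with L = 0.4198, just under the threshold. The PPS could reveal the problem, but it is supportive. It also drops the patient from the denominator instead of scoring a failure (37/70, L = 0.413).

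**7. Power cost of the fix.** If the assumed 60% had included such patients, the rate becomes 0.60 − k/70. Power at n = 70 is then 86.4% for k = 0, 80.3% for k = 1 (rate 0.5857) and 72.8% for k = 2 (rate 0.5714).

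**The case against.** The strongest reply is that the design already closes most of the gap. Under protocol 5.7 and 6.1.4, a 1.0 g/kg patient who is unchanged at Week 6, or who deteriorates after Week 3 and before Week 18, receives NewGam rescue and is a non-responder. Later deterioration means dropping out. An unrescued patient beyond Week 6 should therefore already have improved. That leaves two main routes: forbidden therapy in the first six weeks, or a Week 6 improver who loses the gain without triggering rescue and regains it on other therapy. The second route is open if deterioration is measured from Week 0. SAP 8.4 measures worsening that way; protocol 5.7 does not name the reference point. This argument stands and makes the event less likely, but it does not remove it.

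A reader might infer that every forbidden-therapy user still in the trial at Week 24 adds a false response. The documents do not support that. A patient who had already improved on NewGam and later took a forbidden drug may be a true responder, and many users would be rescued or withdrawn and so already fail.

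It can also be said that using observed outcomes in an intention-to-treat set is a recognised choice and that the PPS analysis tests robustness to deviations. Both are fair. But the SAP has already chosen a composite rule for added treatment, and the PPS depends on case-by-case classification of deviations.

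Finally, the 42% comes from two earlier trials (ICE and PRIMA), and the documents do not say how those trials scored prohibited therapy. Whether a stricter rule makes the comparison more or less like-for-like cannot be settled here.

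**Conclusion.** The gap in wording is real. NewGam rescue is the only treatment that SAP 8.4 itself turns into non-response, and an improved, unrescued patient on other forbidden CIDP therapy counts towards the confirmatory rate.

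Its practical size is unknown. The rise from 2.6% to 4.4%–16.3% rests on an assumed average of 1 to 4 falsely counted patients among 70 and a true rate of exactly 42%. It should not be read as the trial's actual error rate, because nothing in the documents says how often this happens. What needs no assumption about frequency is that one patient can decide the result at 38 versus 37 of 70. This is a cheap improvement to the plan, not a defect that invalidates the test.

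**What to change.** In SAP 8.4, with a matching line in 10.1, extend the No clause of the INCAT, grip strength, I-RODS and MRC response definitions. It should cover patients who received CIDP-active therapy forbidden by protocol 4.2.3 between Week 0 and the assessment. State that therapy the protocol permits does not count: stable azathioprine under 4.2.1 and corticosteroids within 4.2.2. The general wording on immunosuppressants in 4.2.3 must be reconciled with 4.2.1 for this purpose.

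Identify these patients individually by drug, dose, dates and procedures at the blinded data review before database lock. The drug coding in SAP 9.3 is not enough alone: it does not by itself show a dose above the limit, and plasma exchange is a procedure. Protocol 4.2 already requires drug and non-drug therapy to be recorded. Report the present definition as a sensitivity analysis.

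The cost is SAP wording and some case review. The response rate can only stay the same or fall, and a NewGam responder given such therapy for an unrelated reason would be scored a failure. If the assumed 60% had included such patients, the SAP should acknowledge the loss of power from 86.4% to 80.3% or 72.8% for one or two of 70. The change concerns scoring only and alters no clinical rule.

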2.0 g (LD)	0.5g 1.0 g	0.5g 1.0 g	0.5g 1.0 g	0.5g 1.0 g	2.0 g (RT)	2.0 g (RT)	EOS
	2.0 g	2.0 g	2.0 g	2.0 g	EOS		

5. Patients deteriorating* after Week 15 and before Week 18

Week 0	Week 3	Week 6	Week 9	Week 12	Week 15	Week 18	Week 21	Week 24
2.0 g (LD)	0.5g 1.0 g	0.5g 1.0 g	0.5g 1.0 g	0.5g 1.0 g	0.5g 1.0 g	2.0 g (RT)	2.0 g (RT)	EOS
	2.0 g	2.0 g	2.0 g	2.0 g	2.0 g	EOS		

LD – Loading Dose, RT – Rescue Treatment, EOS – End-of-Study-Visit

* = adjusted INCAT disability score increase of at least 1 point

** = adjusted INCAT disability score remains unchanged

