6.1.4 Procedures during the Rescue Treatment

This section is only applicable for patients in the 0.5 and 1.0 g/kg NewGam arms, namely

- a) for patients deteriorating after Week 3 and before Week 18 or
- b) for patients being stable until Week 6

Depending on the time point when deterioration is detected or at Week 6 for patients remaining stable, the Rescue Treatment is initiated.

During the Rescue Treatment patients receive two doses of 2.0 g/kg NewGam in a 3-week interval; first dose at the visit when the deterioration is detected, or at the visit in Week 6 for patients remaining stable, the second dose three weeks later.

Please refer to [Section 5.5](#) for an overview on dosing if a Rescue Treatment is required.

Visit procedures at the Rescue Treatment follow essentially the same process as described for corresponding visits.

Three weeks after the second rescue dose the study termination visit is performed.

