9.1 Determination of Sample Size

The sample size calculation is based on the proportion of responders in the 1.0 g/kg dose group. This dose regimen is the currently most commonly used for maintenance IGIV doses in CIDP. Recent experiences with this dosing regimen are available from the ICE study [24] and the PRIMA trial.[25] In both of these studies, the lower confidence limit of the 95% Wilson-Score confidence interval for the proportion of responders (R) was 42% if rounded to the nearest integer, and thus we have also chosen 42% as the threshold for the following pair of hypotheses for evaluation of the primary endpoint:

[figure not shown]
$$H_0: R < 0.42$$

$$H_1: R \geq 0.42$$

This will be tested by comparing the lower limit of the 95% Wilson-Score confidence interval for the observed proportion of responders with the pre-defined threshold of 0.42.

We estimate the true percentage of responders in CIDP patients treated with NewGam as 60%. This corresponds to the 60.7% of responders observed in the PRIMA study, but is higher than the outcome in the ICE (54.2%), that in the opinion of many experts underestimates the true percentage of responders.

We applied these parameters to a computer simulation realized in SAS to determine the statistical power associated with various group sizes:

To achieve a power of at least 80%, a minimum of 62 evaluable patients in the 1.0 g/kg dose group will be needed; to account for possible dropouts we plan to enroll 70 patients into this group.

In order to allow for the comparison between dose groups, ProCID will enroll half of the eligible patients in the standard dose arm (1.0 g/kg NewGam) and the other half into the lower and higher dose arms (0.5 g/kg and 2.0 g/kg NewGam), resulting in a total of 124 evaluable patients, and an enrollment target of 140 patients overall (ratio: 1:2:1 for 0.5 g/kg, 1.0 g/kg, and 2.0 g/kg, respectively).

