3.2.2. Secondary and Exploratory Target Variables

Efficacy

- Proportion of responders in the 0.5 g/kg and 2.0 g/kg NewGam arms at Week 24 relative to baseline at Week 0 compared to the 1.0 g/kg arm, based on the adjusted INCAT disability score
- Proportion of responders in the 0.5 g/kg and 2.0 g/kg NewGam arms at Week 24 relative to baseline at Week 0 compared to the 1.0 g/kg arm, based on the grip strength (Martin Vigorimeter) using the previously published minimum clinically important difference (MCID) cut-off of 8 kPa
- Proportion of responders in the 0.5 g/kg and 2.0 g/kg NewGam arms at Week 24 relative to baseline at Week 0 compared to the 1.0 g/kg arm, based on the I-RODS scores using the MCID concept related to the varying standard errors (MCID-SE) as recently demonstrated (please refer to protocol)
- Time to first confirmed worsening on the adjusted INCAT disability scale by at least 1
 point or more from the value at Baseline
- Mean change from Baseline (Week 0) to Termination Visit in
 - grip strength of both hands (assessed by Martin Vigorimeter)
 - Inflammatory Rasch-built overall disability sum score (I-RODS using the concept of MCID-SE as recently reported; Appendix 1) and number of improvers
 - sum of the distal evoked amplitude of 4 right sided and 4 left sided motor nerves (peroneal, tibial, ulnar and median)
 - Pain Intensity Numeric Rating Scale (PI-NRS)
- Time to first confirmed worsening on the I-RODS scale
- o Time to 1 point decrease (improvement of disability) in adjusted INCAT disability score
- Time to decrease in I-RODS scores
- o Mean change from baseline (Week 0) to Termination Visit in:
 - modified Fatigue Severity Scale (FSS)
 - SF-36 Health Survey physical composite score (PCS), mental composite score (MCS) and their 8 health domains
 - Additional nerve conduction studies (NCS) analyses (e.g. individual nerve analysis)
- o For MRC the following will be done:
 - Time to decrease in MRC sum score to or below baseline value after temporary improvement (increase)
 - mean change from baseline (Week 0) to Week 12 and to Termination Visit
 - number of improvers by at least 4 points from baseline (Week 0) to Week 12
 and to Week 24

Safety:

- o Throughout the entire 24-week Dose-evaluation Phase:
- Occurrence of all adverse events (AEs)
- Short term tolerance parameters including vital signs
- Physical/neurological examination

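### Time to first adjusted INCAT response is censored by non-response itself; on actual dates the final Kaplan-Meier value would overstate the proportion responding before rescue or drop-out, mostly in a thin tail

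*SAP*

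**What the plan says.** SAP 3.2.2 lists as a secondary or exploratory variable "Time to 1 point decrease (improvement of disability) in adjusted INCAT disability score"; protocol 3.1.2 lists it as secondary. SAP 10.1 presents time to first response by Kaplan-Meier and names no competing-event method.

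SAP 8.4 gives the censoring rule. For rescued patients without an earlier response: "Time to first response will be censored at start date of rescue medication if a patient received rescue medication". For patients with neither response nor rescue, "time to first response will be censored at termination visit". In the same bullet, the Week 24 responder variable is "No otherwise (including patients discontinued before week 24 and patients receiving rescue treatment").

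The triggers are in the design sections:

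- Patients on 0.5 or 1.0 g/kg are rescued if stable at Week 6 or if they deteriorate (SAP 4.1; protocol 3.3.1 and 5.5).
- "Patients in the 2.0 g/kg NewGam arm will drop-out if they are stable at Week 6", and likewise if they deteriorate. Their end-of-study visit in that case is the Week 6 visit (protocol 5.5, first schedule).
- Stable means "adjusted INCAT disability score remains unchanged" (protocol 5.5, footnote).
- Rescue starts with the "first dose at the visit when the deterioration is detected, or at the visit in Week 6 for patients remaining stable" (protocol 6.1.4).

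**The concern.** Kaplan-Meier assumes that a patient censored at a given time has the same future chance of response as those still at risk. Here patients are censored because they were assessed on the endpoint's own scale and found not to have responded. If the protocol is followed, everyone has either responded or been censored by the Week 6 visit.

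Whether this distorts the curve depends on the time scale. The SAP does not state it, although the reference to a start date points to calendar dates. On nominal days, all Week 6 responses and all Week 6 censorings are tied, events are counted first, and nothing is lost. On actual dates, non-responders seen early in the Week 6 window leave the risk set before responders seen later in it. Each later response then carries too much weight.

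At stake is a listed secondary endpoint shown by dose group. Two programmers following the same text could report clearly different plateaus from the same data.

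**Working it through.** **Inputs**

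- Response proportion, from protocol 9.1: "We estimate the true percentage of responders in CIDP patients treated with NewGam as 60"%. Anyone unchanged or worse at Week 6 is rescued or leaves and counts as a Week 24 non-responder. Every Week 24 responder must therefore already be improved at Week 6, so 60% implies at least 60% first response by then.
- Week 3/Week 6 split: protocol 3.3.1 says that about half of IGIV responders improve after the loading dose. This supports 30% at Week 3 and 30% at Week 6; other splits are run as sensitivity cases.
- Visit tolerance: ±4 days (protocol 5.5, 6.1.5). How visits spread within it is not given. An even spread over whole days is assumed.
- Arm size: 70 enrolled on 1.0 g/kg, so 35 in each other arm at 1:2:1.
- Rescue or drop-out is dated to the day of the Week 6 assessment.

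The plan gives no Kaplan-Meier figure to reproduce. Its sample size, which uses the same 60%, does reproduce: with 62 patients the Wilson rule needs at least 34 responders and has 83.1% power; with 61 it has 79.2%.

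**Formula**

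Let r3 and r6 be the proportions first responding at Week 3 and Week 6, m the number of whole days in the Week 6 window, and q = r6/(1 − r3). With k days of the window left, (1 − r3)·k/m of the arm is at risk and r6/m responds, so the daily hazard is q/k. In expected counts:

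final 1 − KM = 1 − (1 − r3) × ∏(k = 1 to m) (1 − q/k)

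**Central case, 30/30, ±4 days (m = 9)**

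q = 0.30/0.70 = 3/7. The product is 0.571 × 0.786 × 0.857 × 0.893 × 0.914 × 0.929 × 0.939 × 0.946 × 0.952 = 0.247. Final value: 1 − 0.70 × 0.247 = **82.7%**. Simulation (4,000 runs, n = 70) gives a mean of 82.6%, SD 8.1 points.

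**Nominal days (m = 1)**

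1 − 0.70 × (1 − 3/7) = 1 − 0.40 = **60%**, with no bias.

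**Other splits at 60%**

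| Week 3/Week 6 | Nominal | ±1 day | ±4 days |
|---|---|---|---|
| 50/10 | 60% | 66% | 73% |
| 40/20 | 60% | 70% | 79% |
| 30/30 | 60% | 73% | 83% |
| 20/40 | 60% | 75% | 85% |

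Protocol 6.1.5 sets the tolerance on the interval between visits, so Week 6 can drift by up to 2 × 4 = 8 days. Simulation then gives 89% (30/30) and 85% (40/20).

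**Other response levels, ±4 days**

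70% (35/35) gives 90%; 80% (40/40) gives 95%; 50% (30/20) gives 71%; 40% (30/10) gives 54%.

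**Where the excess lies (30/30, ±4 days, n = 70)**

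| Day | 1 − KM | Responded so far | At risk |
|---|---|---|---|
| 42 | 50% | 47% | 27 |
| 45 | 70% | 57% | 11 |
| 46 | 83% | 60% | 5 |

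If the curve stops once fewer than 10 are at risk, the mean end value is 68% for n = 70 and 56% for n = 35. The median is Day 43 under the SAP rule and also with non-responders held to Day 168; for 40/20 it is Day 41 against Day 42.

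**Lag between assessment and recorded rescue start (30/30, ±4 days)**

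A lag of 1, 2 or 4 days gives 75%, 70% or 64%.

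**Check of the fix**

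On the same simulated dates, Aalen-Johansen returns 60.0% (30/30) and 60.1% (40/20). With 8 of 70 random withdrawals before Week 6, the 30/30 case still returns 60.0%, against 82.6% for 1 − KM.

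**The case against.** **The bias is conditional.** It vanishes on nominal visit days, and the companion rule refers to a visit, not a date. This stands: a reader might infer that the SAP's curve is biased however it is programmed, and the documents do not support that. They leave the time scale open, which is itself a gap.

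**83% is a tail value.** It is reached with about 5 of 70 at risk, and a 35-patient arm cut off at 10 at risk shows no overstatement. It also needs an even ±4-day spread and no lag before rescue. This stands too. Infusion visits take two days (flowchart footnote 2). No lag is stated, but a short one removes much of the excess. The figure should be read as one case in a range.

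**The target is not the SAP's.** The SAP never says that the curve estimates first response before rescue or drop-out. Censoring at rescue could aim at response had rescue not been given, for which 60% need not be the true value. This is fair, and it is why the target must be written down. It does not rescue the rule: Kaplan-Meier cannot estimate that quantity validly when those censored are exactly the patients just found not to have responded.

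**The plateau and the Week 24 proportion may differ anyway.** First response at any visit and response at Week 24 are different quantities, so a patient who responds and later deteriorates counts in one and not the other. Some disagreement would remain after the fix. Likewise, the flat curve after Week 6 comes from the rescue design and the fix leaves it flat.

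**Little depends on it.** The endpoint is descriptive, and SAP 10.1 also shows responder proportions with rescue and drop-out counted as non-response. This limits the priority, not the correctness.

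**Conclusion.** The concern holds in a limited form. The censoring is informative by construction, and neither document corrects it. On nominal days the final value is right. On actual dates, at 60% response, n = 70 and rescue on the assessment day, it averages about 70% to 89% in the main cases. It is about 83% with half of the responders improved by Week 3 and an even ±4-day spread. Extreme splits fall outside this range (66% for 50/10 at ±1 day), and a 1- to 4-day lag before rescue brings the central case down to 75% to 64%. Only the even spread of days and the no-lag dating lack support in the documents.

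Two further inferences are not supported. The primary Wilson test and its sample size are not affected, because rescued and discontinued patients count as non-responders there. And the same size of error cannot be assumed for I-RODS, grip strength or MRC: SAP 10.2 plans similar analyses without saying which censoring rule applies, and rescue is triggered by INCAT, not by those scales. The size of any bias there is not established.

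**What to change.** In SAP 8.4 and 10.1:

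1. Define the target as first response before rescue or efficacy drop-out.
2. Report Aalen-Johansen cumulative incidence with rescue or efficacy drop-out as a competing event, or keep these patients in the risk set as non-responders to Day 168.
3. Censor only other withdrawals, classified by recorded reason before unblinding. Protocol 4.4.1 recognises that consent may be withdrawn because treatment is not working, so the reason matters.
4. State whether time is nominal visit day or actual date.
5. Show numbers at risk by visit under each curve.

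In SAP 10.2, state the rule for the I-RODS, grip strength and MRC response curves.

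Cost: a few lines of SAP text, a little programming and one blinded classification of withdrawal reasons, using data already collected. If actual dates would have been used, the response curves will look less favourable.
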